### **5. OUTCOMES**

#### **5.1 Primary Outcome**

The **primary outcome** is clinical status on the Modified COVID Ordinal Outcomes Scale to Day 15, incorporating more granular description of symptoms at the milder end of the scale for this outpatient trial. In addition, we collapsed non-invasive ventilation with mechanical ventilation and high flow nasal oxygen with supplemental oxygen to improve pragmatism of in-hospital data collection (source data may come from the patient or alternate contact if hospital records are not accessible). This outcome is in use by COVID-19 trials globally, including those conducted by the World Health Organization, and will facilitate pooling and comparison of data across trials.

##### **1. Death**

2. Hospitalized on mechanical ventilation or ECMO
3. Hospitalized on supplemental oxygen
4. Hospitalized not on supplemental oxygen
5. Not hospitalized with symptoms and limitation in activity
6. Not hospitalized with symptoms but with no limitation in activity
7. Not hospitalized without symptoms or limitation in activity

## 5.2 Secondary Outcomes

- Modified COVID Ordinal Outcome Scale at Study Day 8
- Modified COVID Ordinal Outcome Scale at Study Day 29
- Proportion of patients hospitalized to Study Day 29
- Time to hospitalization to Study Day 29
- Time to symptom resolution to Study Day 29
- All-cause, all-location mortality to Study Day 29
- Oxygen-free days through Study Day 29
- Fever-free days to Study Day 29
- Ventilator-free days through Study Day 29
- Vasopressor-free days through Study Day 29
- ICU-free days through Study Day 29
- Hospital-free days through Study Day 29

## 5.3 Safety outcomes

- Seizure
- Atrial or ventricular arrhythmia
- Cardiac arrest
- \*Elevation in aspartate aminotransferase or alanine aminotransferase to twice the local upper limit of normal, AND at least doubling over known baseline
- \*Acute pancreatitis
- \*Acute kidney injury by KDIGO criteria
- Receipt of renal replacement therapy
- \*Symptomatic hypoglycemia
- \*Anemia or thrombocytopenia
- \*Severe dermatologic reaction

\*For participants whose symptoms are significant enough to trigger a clinical work-up and thus have clinically available testing and diagnoses:

## 5.4 Rationale for Primary Outcome

COVID-19 has a broad spectrum of clinical severity. Among non-hospitalized patients, most recover without experiencing critical illness. Designing a trial with statistical power to detect a meaningful difference in hospital-free days, ICU-free days, or mortality might require an unfeasibly large sample size and could miss significant morbidity experienced by outpatients with COVID-19. Since the majority of

morbidity from COVID-19 relates to hypoxemia, the fact that this outcome is tied to degree of hypoxic respiratory failure increases its face validity and relevance. For similar reasons, previous trials of severe influenza have employed a similar ordinal outcome. This ordinal scale was selected as an outcome in multiple ongoing COVID-19 trials across a range of illness severity, including outpatients, and is a preferred outcome by the World Health Organization Research and Development Blueprint for COVID-19. For our cohort of outpatients, we have enhanced the outcome with the addition of COVID-related symptoms to better distinguish recovery in those with milder disease. Use of this standardized outcome will increase the potential to compare the results of this trial with other trials and perform meta-analyses.

## 6. DATA COLLECTION

Given the infectious risk from COVID-19 and potential shortages of personal protective equipment (PPE), we will have no face-to-face contact between patients and non-clinical staff. Additionally, minimizing research activities and conducting the trial in a pragmatic manner will increase the ability to complete the trial in the face of strained clinical and research resources during the COVID-19 pandemic. We will emphasize data collection by electronic methods, supplemented by telephone or videophone follow-up and from the electronic health record. If the patient is hospitalized, we will attempt to obtain permission for accessing these records. We will not collect biological specimens as part of this trial.

### Electronic Data Collection:

We will collect data directly from patients using MyCap or, if installation and use of an app is not possible, through text messaging or email with a survey link, or phone call as back up. MyCap is a secure mobile application developed by the REDCap team at Vanderbilt and integrated into the REDCap database system. Participants install the application on their personal device. All interaction with the app is secure and requires the user to enter a 6-digit pin. Once a patient has consented, they join a study for data collection by scanning a unique QR code. Then, patients receive a notification each day to answer questions about their current symptom burden, any hospitalizations, and any oxygen requirements. This provides the capacity for collecting patient reported outcomes in a secure and robust manner. If patients are unable to use this application or unwilling to install it, they can be asked the same messages using a text messaging system will be utilized. Our outcomes are designed such that a text messaging option is not overly burdensome and can even be completed in hospitalized patients. The process for using text messaging is HIPAA compliant. Finally, we can use standard telephone calls as a back-up method to administer the questions. This minimizes loss to follow up and maximizes the efficiency of the study. Research teams have had great success using REDCap-based mobile data collection for multiple studies including collection of data about quality of life and exercise after heart surgery (NCT03270124), pain reporting in sickle cell disease (NCT03629678), and pain using a visual analog scale (VAS) during an interventional drug study (NCT03865940).

### Telephone/Videophone Data Collection:

While primary data collection will be by electronic methods as above, specific circumstances will trigger telephone or videophone follow-up, based on the following:

- Participant does not complete daily electronic data collection for two consecutive days.
- Participant does not complete Study Day 29 assessment
- Identification of newly prescribed medication if deemed necessary by site investigator.
- New electrocardiogram

- Lack of administration of study medication, if unable to confirm plan to resume study medication
- Hospitalization
- Reported adverse events, if deemed necessary by the site investigator
- Clarification or concern by study team
- By request of participant

## 6.1 Baseline Variable Collection

- Informed Consent Document and documentation of consent process
- Presence or absence of each inclusion and exclusion criterion
- Date and time of enrollment
- Day of symptom onset
- Specimen type, date, and result of SARS-CoV-2 testing conducted clinically.
- Demographics (age, sex, race, ethnicity, height, weight)
- Comorbidities: chronic cardiac disease, chronic pulmonary disease, chronic kidney disease, chronic liver disease, chronic neurological disease, malignant neoplasm, chronic hematologic disease, AIDS/HIV, obesity, diabetes with complications, diabetes without complications, rheumatologic disorder, malnutrition, smoking, other
- Chronic use of medication: ACE inhibitors, angiotensin receptor blockers
- Receipt of azithromycin in the past week
- Presenting signs and symptoms, along with self-reported severity

## 6.2 Daily Assessments between Randomization and Study Day 16, and then at Day 29

- Study drug administration and reason for missed doses.
- Modified COVID Ordinal Outcomes Scale
- Daily signs and symptoms, along with self-reported severity via electronic log and/or telephone interview.
- Day of symptom resolution
- Receipt of open label antivirals: chloroquine, hydroxychloroquine, remdesivir, lopinavir/ritonavir, other
- Receipt of open label immunomodulators between enrollment and hospital discharge: corticosteroids, tocilizumab, sarilumab, interferon  $\beta$ , other
- Receipt of azithromycin
- Study days in hospital (if applicable)
- Study days receiving supplemental oxygen (if applicable)
- Study days receiving non-invasive or invasive mechanical ventilation (if applicable)
- Study days in ICU to Study Day 29
- Study day of death (if applicable)
- Safety Outcomes: seizure, atrial or ventricular arrhythmia, cardiomyopathy, cardiac arrest, aspartate aminotransferase or alanine aminotransferase levels that are greater than twice the local upper limit of normal (or two times higher than known baseline), acute pancreatitis (defined by a clinically obtained lipase level above the local upper limit of normal and abdominal pain or vomiting), stage II or greater acute kidney injury according to KDIGO criteria, receipt of new renal replacement

therapy, symptomatic hypoglycemia, neutropenia, lymphopenia, anemia, thrombocytopenia, or severe dermatologic reaction (e.g., Steven's Johnson Syndrome). Since we will not systematically obtain laboratory tests to identify asymptomatic changes in laboratory values, we will ask about outpatient laboratory testing or obtain the requisite results of laboratory tests from medical records if tests were obtained.

- Prolonged (>500 msec) QTc interval on available electrocardiograms
- Self-reported adverse events to Study Day 15

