Randomization	Eligible patients will be randomized through a central electronic system in a 1:1 ratio, to lopinavir/ritonavir (intervention) versus placebo (control). Randomization will be stratified by site and age ( $\geq 65$ years or $< 65$ years).
Blinding	Patients, treating clinicians, trial personnel, and outcome assessors will be blinded to group assignment.
Primary Outcome	Modified COVID Ordinal Outcomes Scale to Study Day 15: 1. Death

	
 
2. Hospitalized on mechanical ventilation or ECMO
 
3. Hospitalized on supplemental oxygen
 
4. Hospitalized not on supplemental oxygen
 
5. Not hospitalized with symptoms and limitation in activity
 
6. Not hospitalized with symptoms but with no limitation in activity
 
7. Not hospitalized without symptoms nor limitation in activity
 

Secondary Outcomes	
 
• Modified COVID Ordinal Outcome Scale to Study Day 8
 
• Modified COVID Ordinal Outcome Scale to Study Day 29
 
• Proportion of patients hospitalized to Study Day 29
 
• Time to hospitalization to Study Day 29
 
• Time to symptom resolution to Study Day 29
 
• All-cause, all-location mortality to Study Day 29
 
• Oxygen-free days through Study Day 29
 
• Fever-free days to Study Day 29
 
• Ventilator-free days through Study Day 29
 
• Vasopressor-free days through Study Day 29
 
• ICU-free days through Study Day 29
 
• Hospital-free days through Study Day 29
 

Safety Outcomes	
 
• Seizure
 
• Atrial or ventricular arrhythmia
 
• Cardiac arrest
 
• *Elevation in aspartate aminotransferase or alanine aminotransferase to twice the local upper limit of normal AND at least doubling over known baseline
 
• *Acute pancreatitis
 
• *Acute kidney injury by KDIGO criteria
 
• Receipt of renal replacement therapy
 
• *Symptomatic hypoglycemia
 
• *Anemia or thrombocytopenia
 
• Severe dermatologic reaction
 
 
*For participants whose symptoms are significant enough to trigger a clinical work-up and thus have clinically available testing

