Safety outcomes to be included in the safety analysis for this trial include all potentially associated adverse events (PAAEs) as well as other events of interest including, but not necessarily limited to:

- Seizure
- Atrial or ventricular arrhythmia
- Cardiac arrest
- Receipt of renal replacement therapy

- Severe dermatologic reaction
- *Elevation in aspartate aminotransferase or alanine aminotransferase to twice the local upper limit of normal AND at least doubling over known baseline
- *Acute pancreatitis
- *Acute kidney injury by KDIGO criteria
- *Symptomatic hypoglycemia
- *Anemia or thrombocytopenia

* For participants whose symptoms are significant enough to trigger a clinical work-up and thus have clinically available testing

6 Study Methods

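### The liver and kidney safety outcomes are defined one way where they are collected (Protocol 6.2) and another way where they are listed and analysed (Protocol 1 and 5.3, SAP 5.3)

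*Protocol*

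**What the plan says.** **Collection.** The safety item in Protocol 6.2 asks for AST or ALT "greater than twice the local upper limit of normal (or two times higher than known baseline", and for "stage II or greater acute kidney injury according to KDIGO criteria".

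**Outcome lists.** Protocol 5.3 requires AST or ALT to reach "twice the local upper limit of normal, AND at least doubling over known baseline". The Protocol 1 summary says the same, and SAP 5.3 repeats it: "Elevation in aspartate aminotransferase or alanine aminotransferase to twice the local upper limit of normal AND at least doubling over known baseline". For the kidney, Protocol 5.3 lists "Acute kidney injury by KDIGO criteria". Protocol 1 and SAP 5.3 match it, and none of the three gives a stage limit.

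**Source of laboratory values.** Protocol 6 states that no biological specimens are taken. Protocol 6.2 adds that "we will not systematically obtain laboratory tests to identify asymptomatic changes in laboratory values". Staff will ask about outpatient testing or "obtain the requisite results of laboratory tests from medical records if tests were obtained". AST, ALT and creatinine are not in the baseline variable list of Protocol 6.1. At eligibility (Protocol 3.2), AST and ALT are checked only where the medical record holds a value, and only values above 3 times the upper limit exclude.

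Both outcomes carry an asterisk in Protocol 5.3 and SAP 5.3, which limits them to participants whose symptoms led to a clinical work-up. Neither document says how to classify an elevation when no baseline is known.

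**The concern.** The two mismatches run in opposite directions. For the kidney, the collection item is narrower than the outcome to be reported. For the liver, it is wider, and the outcome depends on a quantity (a known baseline) that the trial does not generate.

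Both organs matter here. Protocol 9.1.2 names hepatotoxicity among the key safety concerns of the study drug and notes that persistent vomiting or diarrhea may impair renal function. Describing the safety profile is a secondary objective in SAP 5.1. Laboratory-based events can come only from testing done for clinical reasons. If some of those are not collected, or are classified differently by different readers of the plan, the tabulated comparison between arms is weaker and cannot be reproduced from the text.

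**Working it through.** No sample size, power or event-rate figure in the plan bears on this point, so there is nothing to reproduce. The check compares the definitions.

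| Outcome | Collected (Protocol 6.2) | Listed and analysed (Protocol 1, 5.3; SAP 5.3) | Relation |
|---|---|---|---|
| AST/ALT | above 2 × ULN *or* twice known baseline | 2 × ULN *and* at least twice known baseline | collection wider |
| Kidney injury | KDIGO stage II or greater | KDIGO, any stage | collection narrower |

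**Liver.** Let *p* be the on-study value and *b* the baseline, both in multiples of the local upper limit (ULN).

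- Collected if *p* > 2, or if *b* is known and *p* ≥ 2*b*.
- Analysed, read literally, if *p* ≥ 2, *b* is known and *p* ≥ 2*b*.

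Any case that meets the analysed rule has *b* known and *p* ≥ 2*b*, which already meets the second limb of the collected rule. The analysed set is therefore nested in the collected set. A grid confirms this. It used *b* unknown or 0.05 to 3.00 in steps of 0.05 (61 settings) and *p* from 0.05 to 10.00 in steps of 0.05 (200 values), giving 61 × 200 = 12,200 combinations. None was analysed but not collected.

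Examples:

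| Baseline *b* | On-study *p* | Check of *p* against 2*b* | Collected | Analysed |
|---|---|---|---|---|
| 1.0 | 2.5 | 2.5 ≥ 2.0 | yes | yes |
| 1.5 | 2.5 | 2.5 < 3.0 | yes | no |
| 2.5 | 2.5 | 2.5 < 5.0 | yes | no |
| 0.4 | 0.9 | 0.9 ≥ 0.8, but *p* < 2 | yes | no |
| unknown | 2.5 | cannot be evaluated | yes | no |
| unknown | 5.0 | cannot be evaluated | yes | no |

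The third row is an eligible participant with a stable value, since 2.5 is below the exclusion threshold of 3. The last two rows show that, with no prior value, the height of the elevation makes no difference under the literal rule.

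**Kidney.** Stage 1 belongs to the analysed outcome and lies outside the collection item. The remaining route is adverse event reporting. Protocol 11.2 makes three kinds of event reportable: serious events, non-serious events judged related or of uncertain relationship, and events leading to permanent discontinuation of study drug. Protocol 11.2 and Appendix C.3 then exempt study-specific outcomes unless they are judged related or of uncertain relationship. Appendix C.3 names acute kidney injury, with no stage, and AST/ALT elevation as examples. Protocol 11.2 rests the exemption on these outcomes being recorded systematically in the case report forms. Under the 6.2 wording that does not hold for stage 1 kidney injury. A non-serious event that does reach the adverse event forms is tabulated under SAP 11 only if its frequency exceeds 5% in an arm.

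**The case against.** The strongest reply is that Protocol 6.2 is the working layer beneath 5.3. It supplies, for example, a definition of pancreatitis that 5.3 lacks. On that reading stage II or greater is the intended threshold, and the outcome lists are shorthand. This could explain the kidney wording, although nothing in either document says so. It cannot explain *or* in one place against *and* in three others.

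Second, the case report form is not among the documents, so values, limits and stages may already be recorded. If they are, the liver outcome can be derived, because the analysed rule is nested in the collected one. That is a fair point, but the documents do not state it, and it leaves the definition unsettled.

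Third, the doubling condition may be meant to apply only when a baseline is known. The wording does not say that, which is why a rule is needed.

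Fourth, the larger limit on ascertainment is the deliberate choice to draw no study laboratory tests, and the safety analysis in SAP 11 is descriptive. Both are true and both bear on how much weight the point carries. Neither removes the conflict.

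A reader might infer that stage 1 kidney injury is never captured, or that liver events without a baseline never count anywhere. The documents do not support either. Adverse event reporting and the look-up of medical records are partial backstops, the SAP safety list is open-ended, and the liver events do fall within the 6.2 item.

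A reader might also want the multiple of the upper limit alone to decide when no baseline exists. That would count pre-existing elevations as events, since values up to 3 times the limit are eligible and are checked only where a record exists.

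**Conclusion.** The conflict is real and stands on the wording of the two documents. As written, stage 1 kidney injury is not systematically collected, so the any-stage outcome would be incompletely ascertained. An AST/ALT elevation without a known baseline is collected, but on a literal reading it cannot meet the analysed outcome.

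The size cannot be computed. The documents give no laboratory event rates and no share of participants with a prior AST/ALT value, and any percentage would have to be assumed. The relevant share is among participants who had an elevation found in a clinical work-up, and it may differ from the share among all participants.

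The conclusion assumes that 6.2 governs what is recorded and that the listed definitions are applied literally. The grid check also takes the second limb of the 6.2 liver rule to mean at least twice baseline. The primary efficacy analysis is not affected. The point concerns two of ten listed safety outcomes, and it should be settled because it is cheap to settle and cannot be repaired at analysis if the values were not recorded.

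**What to change.** 1. Reconcile Protocol 1, 5.3 and 6.2 and SAP 5.3 to a single definition for each of the two outcomes.
2. Record the underlying data from results already being sought from records: the AST/ALT value, the local upper limit, the baseline if known, and the creatinine or KDIGO stage. Derive both outcomes in analysis.
3. Before unblinding, state in the SAP how an elevation with no known baseline is handled. One option is to report these as a separate category, so that they are neither dropped nor mixed with confirmed doublings.

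The cost is a few form fields and wording changes in both documents. The separate category may include some elevations that were present before the study, and the report should say so.

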22. Currently prescribed (with planned continuation) or planned administration during 14-day study period of any of the following medications: alfuzosin, apalutamide, astemizole, ergot-containing medicines (including dihydroergotamine mesylate, ergotamine tartrate, methylergonovine), lomitapide, lovastatin, lurasidone, midazolam, phenobarbital, phenytoin, ranolazine, rifampin, sildenafil, simvastatin, rivaroxaban, St. John's Wort, terfenadine, triazolam. Patients who are on warfarin or fluticasone will be advised to contact their primary care provider to advise them that they are in the trial and possibly receiving lopinavir/ritonavir which can influence levels of either drug and may require more frequent monitoring.

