### **4.5 On-Study Monitoring**

All participants enrolled in the study will be outpatients (not hospitalized) and therefore initial monitoring will be remote as part of routine outpatient clinical care with treating physicians and nurses (we anticipate primarily virtual care/telehealth or routine telephone follow-up). The research staff will provide additional remote monitoring through daily electronic collection of symptoms, healthcare utilization, clinically obtained electrocardiograms, newly prescribed medications, and adverse event reporting with supplemental telephone follow-up as needed. The research team may flag potential issues but will defer specific decisions about additional care and hospital transfer to usual outpatient clinical care.

Lopinavir/ritonavir has been used extensively for outpatient treatment of other conditions without the need for additional monitoring during short term therapy.

Between baseline and Study Day 15, study personnel will ascertain and review the initiation of any new medications daily and evaluate for potential medication interactions with lopinavir/ritonavir (see Appendix B). If a medication that is considered to be contraindicated with lopinavir/ritonavir is discovered, site physician investigator or designee will contact the patient to discuss if stopping study drug is appropriate or if the medication in question may be stopped or substituted in consultation with the prescribing/treating clinician. If a medication with a potential interaction with lopinavir/ritonavir is identified, study personnel will contact the treating clinician to ensure they are aware of the potential interaction, as needed. Treating clinicians will determine whether an alternative medication would be

appropriate or whether the risk-benefit ratio favors continuing the medication with the known potential interaction.

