#### **4.6 Criteria for Stopping Study Drug**

We will stop administration of the blinded study drug temporarily or permanently for (a) adverse events without evidence of an alternative cause to the patient's symptoms, (b) results of on-study monitoring, or (c) clinical deterioration if requested by treating clinician.

If a patient experiences an adverse event that the patient treating clinicians, or investigators feel merits temporarily or permanently stopping the study drug, we will stop the study drug. We will record the explanation for stopping the study drug in the case report form, and we will record and report the adverse event according to the adverse event guidelines below. If the adverse event resolves to the extent that the patient, treating clinicians, and investigators feel that resuming the study drug is appropriate, we will resume the study drug, and we will record this information in the case report form.

If an EKG is obtained as part of routine clinical care after enrollment and the QTc is greater than or equal to 500 ms, we will discontinue the study drug, unless a repeat EKG after at least 24 hours demonstrates the QTc is less than 500 ms, at which time we will direct the patient to resume the study drug. We will record both the value for the QTc and the decision to continue or stop the study drug in the case report form. If the daily on-study monitoring by study personnel for medication interactions indicates a potential interaction with a medication that treating clinicians feel is required for the optimal treatment of the patient and with which treating clinicians and the investigator feel it would be unsafe to administer lopinavir/ritonavir, we will stop study drug and record the reason in the case report form.

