Important potential risks include PR prolongation at therapeutic dosing, and QT prolongation with supratherapeutic doses. Lopinavir/ritonavir interacts with several drugs since it is an inhibitor of the P450 isoform CYP3A and is likely to increase the plasma concentration of drugs that are metabolized by CYP3A4. Therefore, LPV/r should not be co-administered with drugs primarily metabolized by CYP3A and for which elevated plasma concentrations are associated with serious and/or life-threatening events. A list of such products is included in the lopinavir/ritonavir label. Rare reports of second- or third-degree atrioventricular block in patients with underlying structural heart disease and pre-existing conduction system abnormalities, or in patients receiving drugs known to prolong the PR interval such as verapamil, have been reported in patients receiving lopinavir/ritonavir. Lopinavir/ritonavir should be used with caution in such patients. In addition, QT prolongation with supratherapeutic doses and when lopinavir/ritonavir is co-administered with drugs known to prolong the QT interval has been reported. Because lopinavir/ritonavir is principally metabolized by the liver, caution should be exercised when administering this drug to patients with impaired hepatic function. Extra monitoring is recommended when diarrhea occurs. The relatively high frequency of diarrhea during treatment with lopinavir/ritonavir may compromise the absorption and efficacy (due to decreased compliance) of lopinavir/ritonavir or other concurrent drugs. Serious persistent vomiting and/or diarrhea with lopinavir/ritonavir use might also compromise renal function. The safety of lopinavir/ritonavir for treatment of patients with COVID-19 disease is unknown. COVID-19 may be associated with cardiac effects. lopinavir/ritonavir may prolong QT at supratherapeutic doses and prolong PR at therapeutic doses, resulting in arrhythmias.

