## **Appendix B. Potential medication interactions with lopinavir/ritonavir**

Medications considered to present a potential interaction with lopinavir/ritonavir, which if ordered during the 14-day study period, will prompt study personnel to discuss with treating clinicians the risk-benefit assessment of this medication and potential need for additional monitoring: flecainide, mefloquine, methotrexate, mexilitine, rifampicin, rifapentine, amiodarone, cimetidine, dofetilide, phenobarbital, phenytoin, or sotalol, propafenone, astemizole, terfenadine, alfuzosin, apalutamide, ranolazine, dronedarone, rifampin, lurasidone, cisapride, pimozide, ergot-containing medicines (including dihydroergotamine mesylate, ergotamine tartrate, methylergonovine), lovastatin, simvastatin, lomitapide, sildenafil, triazolam, midazolam, rivaroxaban, fluticasone and anticoagulants or St. John's Wort.

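### The protocol's caution on PR prolongation and AV block has no specific provision behind it: ECG rules use QTc only, AV block is not a named outcome, and verapamil is on no list

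*Protocol*

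**What the plan says.** **The warning.** Protocol 9.1.2 states: "Important potential risks include PR prolongation at therapeutic dosing, and QT prolongation with supratherapeutic doses". The trial uses the standard 400/100 mg twice-daily regimen (4.2), so the PR effect is the one tied to the trial's own dose level. The same section describes rare second- or third-degree AV block in patients with structural heart disease and existing conduction abnormalities, or "in patients receiving drugs known to prolong the PR interval such as verapamil". It concludes: "Lopinavir/ritonavir should be used with caution in such patients".

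**ECG provisions.** No study ECG is required (3.3, 9.2), but ECGs obtained in routine care are collected (4.5). The stopping rule in 4.6 begins "If an EKG is obtained as part of routine clinical care after enrollment and the QTc is greater than or equal to 500 ms", and the data item in 6.2 is "Prolonged (>500 msec) QTc interval on available electrocardiograms".

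**Medication provisions.** Exclusion 21 lists drugs under a QT heading and exclusion 22 lists further prohibited drugs. Exclusion 22 also gives advice without excluding: "Patients who are on warfarin or fluticasone will be advised to contact their primary care provider". During the study, "study personnel will ascertain and review the initiation of any new medications daily", checked against Appendix B, whose drugs are those "which if ordered during the 14-day study period, will prompt study personnel to discuss with treating clinicians the risk-benefit assessment".

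**Safety outcomes.** The rhythm items in Protocol 5.3 and SAP 5.3 are atrial or ventricular arrhythmia and cardiac arrest. AV block is not named.

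**The concern.** The protocol identifies a cardiac risk at the dose it uses, says which patients need caution and gives an example drug. One would expect those patients to be flagged at entry and the event to be visible in the safety data. Section 11 adds to that expectation by presenting review of new medications and clinical ECGs as a way to act before harm occurs.

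As written, a person on long-term verapamil can be enrolled and start 14 days of lopinavir/ritonavir with every instruction followed and no protocol step directing anyone to weigh that combination. If AV block is seen on a clinical ECG, no specific rule or data field applies, whereas a QTc of 500 ms or more has a stated action. The stake is participant safety and the legibility of one class of safety event. Sample size and the primary analysis are not involved.

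**Working it through.** The plan gives no figure to reproduce. The check is whether the warning in 9.1.2 reappears in any operative section of either document.

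**Step 1: specific provisions.**

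| Provision | QT | PR or AV block |
|---|---|---|
| Exclusion by history | Exclusion 18 | none |
| Exclusion by co-medication | Exclusion 21 | none |
| ECG stopping rule | 4.6 | none |
| ECG data item | 6.2 | none |
| Total | 4 | 0 |

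PR interval, AV block and verapamil are mentioned only in Protocol 9.1.2.

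**Step 2: verapamil in the medication lists.**

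- Exclusion 21, by class: 10 + 3 + 4 + 9 + 9 + 7 = 42 drugs; verapamil in 0.
- Exclusion 22: 18 entries; verapamil in 0.
- Appendix B: 34 entries; verapamil in 0.
- Entry advice without exclusion: 2 drugs (warfarin, fluticasone); verapamil is not one of them.

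**Step 3: timing.** Appendix B and the 4.5 review act on drugs started during the study. Adding verapamil to Appendix B alone would still miss a long-term user. Appendix A records home medications at randomization, so the information is available at entry, but nothing links it to the 9.1.2 caution.

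**Step 4: cardiac history.** Conduction disease could be entered at baseline under chronic cardiac disease or under other (6.1). Neither entry triggers a discussion.

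**Step 5: visibility of AV block in the results.**

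- If filed under atrial or ventricular arrhythmia, it is pooled with other rhythm events. If also judged unrelated, it is exempt from adverse event reporting (11.2, Appendix C.3), though still recorded as an outcome.
- If serious and reported, it enters the SAP section 11 table by organ system and arm.
- If reported as a non-serious event, it is tabulated only when its frequency exceeds 5% in an arm. With about 300 per arm, 0.05 × 300 = 15, so at least 16 participants would be needed. An event that the protocol calls rare should not be expected to reach that.

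**The case against.** The best reply is that protection does not depend on naming PR or AV block, and much of it stands. A research physician prescribes for each participant (4.1), with home medications and cardiac history collected; advice to use caution is addressed to such a prescriber. A new ECG triggers telephone or videophone contact whatever it shows (Section 6). Section 4.6 permits stopping for adverse events or on-study monitoring results, and 10.3 lets the investigator or treating physician withdraw a participant. Serious events, and related or uncertain non-serious events, are reportable. The DSMB reviews them and can ask for more monitoring. The SAP 5.3 list is expressly open-ended, so AV block could be tabulated without an amendment.

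A reader might therefore infer from the gap that AV block would go unnoticed or that at-risk patients have no protection. The documents do not support that. What survives is narrower: none of these routes mentions PR, AV block or verapamil, and the stopping and reporting routes act mainly after an event or a clinician's suspicion.

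The sponsor also says in 3.3 that it followed guidance on outpatient prescribing without a baseline ECG. That guidance cannot be seen here, so the omission cannot be called an oversight with certainty. Section 9.2 sets aside transient, clinically insignificant ECG changes, but second- or third-degree block should not be presumed to be either.

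**Conclusion.** The point holds as a gap in implementation: a missing protocol-specified prompt and missing separate identification of AV block. Its measurable size is textual: four QT-specific provisions against none for PR or AV block, and verapamil on none of three lists.

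Three further readings are tempting and are not supported.

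- **A number of affected participants.** The documents give no rate of verapamil use or conduction disease. Assuming 0.5% to 5% of 600 gives 3 to 30, but that only restates the assumption. No AV block rate can be derived either.
- **A wider list of missing PR-prolonging drugs.** The documents name only verapamil and do not classify the listed drugs by PR effect. Ten antiarrhythmics are excluded, on QT grounds.
- **Every patient with structural heart disease is in the caution group.** The wording of 9.1.2 can be read as requiring structural disease and conduction abnormality together.

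The QT provisions are not in question. The conclusion assumes that 9.1.2 states a caution the sponsor intends to apply. The change is worth making because it is cheap and follows a device the protocol already uses.

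**What to change.** 1. Add verapamil to Appendix B and to the entry advice in exclusion 22 beside warfarin and fluticasone. Check it against the home medications recorded at randomization, for all participants regardless of arm, without excluding the patient.
2. Give the prescribing research physician the same prompt when known conduction system disease is reported at entry.
3. In 6.2, record second- or third-degree AV block from the clinical ECGs already reviewed for QTc. Report it by arm as its own line in the safety outcomes (Protocol 5.3, with its copy in the Section 1 summary, and SAP 5.3).
4. Optionally, name new second- or third-degree AV block in 4.6 as an example of an on-study monitoring result that stops study drug. No PR-interval threshold is needed.

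The cost is one drug name in two places, one data item, one safety line, possibly one sentence in 4.6, and a few extra clinician contacts at entry. No tests, visits or exclusions are added. The AV block data will be sparse and descriptive, and without a baseline ECG some blocks may predate the drug.
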